## Appendix F Abbreviations

Abbreviation or special term	Explanation
ADE	Antibody dependent enhancement
AE	Adverse event
AESI	Adverse event of special interest
ALP	Alkaline phosphatase
ALT	Alanine aminotransferase
AST	Aspartate aminotransferase
C1q	Complement component 1q
CI	Confidence interval
CIOMS	Council for International Organizations of Medical Sciences
CONSORT	Consolidated Standards of Reporting Trials
CSP	Clinical Study Protocol
CSR	Clinical Study Report
CTCAE	Common Terminology Criteria for Adverse Events
CTIS	Clinical Trial Information System
DBL	Database lock
DES	Data entry site
DILI	Drug-induced liver injury
ECG	Electrocardiogram
ECMO	Extracorporeal membrane oxygenation
eCRF	Electronic case report form
EDC	Electronic data capture
EU	European union
EUA	Emergency use authorization
FAAN	Food allergy and anaphylaxis network
FAS	Full analysis set
Fc	Fraction crystallizable
FcRn	Neonatal Fc receptor
GCP	Good clinical practice
GMFR	Geometric mean fold rise (GMT ratio of post-treatment titer to baseline titer)
GMT	Geometric mean titer
gSD	Geometric standard deviation
HIV	Human immunodeficiency virus
HL	Hy's law
IC XX	Concentration required for XX% inhibition

Abbreviation or special term	Explanation
ICF	Informed consent form
ICH	International council for harmonisation
IEC	Independent ethics committee
Ig	Immunoglobulin
IL-D	Illness day
IM	Intramuscular
IMP	Investigational medicinal product
IRB	Institutional review board
IWRS	Interactive web response system
MAAE	Medically attended adverse event
mAb	Monoclonal antibody
MedDRA	Medical dictionary for regulatory activities
nAb	Neutralizing antibody
NIAID	National institute of allergy and infectious disease
NIMP	Non-investigational medicinal product
NIV	Non-invasive ventilation
PEF	Peak expiratory flow
PHL	Potential Hy's law
PK	Pharmacokinetics
QTL	Quality tolerance limit
RBD	Receptor-binding domain
RNA	Ribonucleic acid
RT-PCR	Reverse transcription polymerase chain reaction
SAE	Serious adverse event
SAP	Statistical analysis plan
SARS-CoV-2	Severe acute respiratory syndrome coronavirus 2
SoA	Schedule of activities
SpO 2	Oxygen saturation
SUSAR	Suspected unexpected serious adverse reaction
TBL	Total bilirubin
TM	L234f/l235e/p331s substitutions in the immunoglobulin heavy chain to reduce fc receptor and c1q binding
ULN	Upper limit of normal
US	United states of America
VOC	Variant of concern

Abbreviation or special term	Explanation
WHO	World health organization
WOCBP	Woman of childbearing potential
YTE	M252Y/S254T/T256E substitutions in the immunoglobulin heavy chain to increase FcRn affinity that results in the increased half-life of an antibody

## **Appendix G Forms of Early Safety Data Review (ESDR) Decision by the Safety Assessment Committee in the SUPERNOVA Study**

These forms are appended as separate documents.

## **Appendix H Protocol Version History**

The Summary of Changes Table for the current revision is located directly before the Table of Contents.

4.3.4.1	Definitions and Derivations	22
4.3.4.2	Presentations	22
4.3.5	Electrocardiogram and Physical Examination.....	22
4.3.5.1	Definitions and Derivations	22
4.3.5.2	Presentations	22
4.3.6	Liver Signs and Symptoms	22
4.3.6.1	Presentations	22
5	INTERIM ANALYSIS	23
6	REFERENCES	24
	APPENDIX A MISSING MEDICATION DATES IMPUTATION	24
	APPENDIX B MISSING SAFETY DATA	24
	APPENDIX C MISSING DATA ON NEUTRALIZING ANTIBODIES	25
	APPENDIX D AESI – PT MAPPING	25

LIST OF ABBREVIATIONS

Abbreviation or Specialized Term	Definition
AE	Adverse Event
AESI	Adverse Event of Special Interest
ALT	Alanine Aminotransferase
AST	Aspartate Aminotransferase
ATC	Anatomical Therapeutic Class
BMI	Body Mass Index
CI	Confidence Interval
COVID-19	COronaVIrus Disease
CSP	Clinical Study Protocol
ECG	Electrocardiogram
eCRF	Electronic Case Report Form
FAS	Full Analysis Set
GCP	Good Clinical Practice
GFR	Glomerular Filtration Rate
Gm	Geometric Mean
GMFR	Geometric Mean Fold Rise (GMT Ratio of Post-Treatment Titer to Baseline Titer)
GMT	Geometric Mean Titer
gSD	Geometric Standard Deviation
ICF	Informed Consent Form
ICH	International Council for Harmonisation
IMP	Investigational Medicinal Product
IPD	Important Protocol Deviation
LLN	Lower Limit of Normal
M	Mean
MAAE	Medically Attended Adverse Event
max	Maximum
Me	Median
MedDRA	Medical Dictionary for Regulatory Activities
min	Minimum
N	Number of (Valid) Observations
NA	Not Applicable

Abbreviation or Specialized Term	Definition
nAb	Neutralizing Antibody
PD	Protocol Deviation
PDMP	Protocol Deviations Management Plan
PT	Preferred Term
Q1–Q3	1 st And 3 rd Quantiles
RT-PCR	Reverse Transcription Polymerase Chain Reaction
SAE	Serious Adverse Event
SAP	Statistical Analysis Plan
SARS-CoV-2	Severe Acute Respiratory Syndrome Coronavirus 2
SAS	Software for Statistical Analysis
SD	Standard Deviation
SOC	System Organ Class
TBL	Total Bilirubin
ULN	Upper Limit of Normal
WHO	World Health Organization
WHO Drug	World Health Organization Drug Dictionary

AMENDMENT HISTORY

Change refers to:	Date	Description of change	In line with CSP?	Rationale
N/A	10/12/2023	Initial approved SAP	NA	NA
4.1.6.1	19/02/2024	Description of calculation of “time (days) from last COVID-19 infection reported” added	YES	Clarification
4.1.7.2	19/02/2024	Description of table of prior COVID-19 infections removed	YES	This table described in section 4.1.6.1
4.2.1.3	19/02/2024	In description of tables of AESIs the SOC replaced with category	YES	Category is more informative for AESI than SOC
4.2.1.3	19/02/2024	Description of listings of AEs of participants who died, who had serious AEs and who discontinued study removed, description of listing of AEs leading to death added.	YES	Decided that these listings are redundant, to present AEs leading to death will be more suitable.
4.2.2.3	19/02/2024	Clarified that outputs of SARS-CoV-2 Neutralizing Antibody assessments will be presented separately for each dominant variant	YES	Clarification
4.2.3.3	19/02/2024	Clarification of table of symptomatic COVID-19 cases.	YES	Clarification
4.3.1.2	19/02/2024	Presentation of cases of IP administration interruption	YES	Clarification
4.3.3.2	19/02/2024	Description of shift tables for blood parameters updated: the table will be based on maximum CTCAE grades separately for low and high abnormal results	YES	Such presentation of abnormal results is more informative and suitable.
4.3.4.1	19/02/2024	The rules of dealing with multiple VS measurements added.	YES	Clarification
4.3.5.2	19/02/2024	Description of listing of physical examination removed.	YES	Physical examination findings register and present as AEs
5	19/02/2024	The rule of selecting data for the interim analysis added. Typos corrected	YES	Clarification
3.3.1	24/06/2024	The rule of rounding log-transformed data is added	YES	Clarification
4.1.5.1	24/06/2024	Presentation of number of participants previously vaccinated is added	YES	Clarification
4.2	24/06/2024	Typos in section numbers in the table were corrected	YES	Clarification

CSP – clinical study protocol; NA – not applicable; SAP – statistical analysis plan.

1 INTRODUCTION

The purpose of the current statistical analysis plan (SAP) is a detailed (in comparison to Section 9 of the Clinical Study Protocol (CSP)) description of basic principles of statistical analysis, description of methods used to analyse the primary and secondary endpoints, and other data obtained during the study.

This plan provides for compliance of the planned and conducted statistical analysis with the CSP, including the definition of data sets for analysis, transformations and calculations for endpoints, the required number of observations, etc. All discrepancies with the CSP should be clarified.

The current statistical analysis plan is prepared in compliance with:

- ICH harmonised tripartite guideline. Statistical principles for clinical trials (E9). Step 5 finalized guideline February 1998
- ICH harmonised tripartite guideline. Structure and Content of Clinical Study Reports (E3). Step 5 finalized guideline dated November 1995
- Good Clinical Practice of the Eurasian Economic Union, adapted by the decision of the Council of Eurasian Economic Commission on 3 November 2016, N 79
- Recommendation of the Board of the Eurasian Economic Commission No. 19 "On Guidelines for the Application of Biostatistics principles in Clinical trials of Medicinal Products", dated 3 November 2020

This SAP is based on version 3.0 of the CSP dated 2 August 2023. In case of future amendments to the protocol, the SAP may be modified to account for changes relevant to the statistical analysis.

2 CHANGES TO PROTOCOL PLANNED ANALYSES

Not applicable for the current version of statistical analysis plan.

3 DATA ANALYSIS CONSIDERATIONS

3.1 Timing of Analyses

An interim analysis is planned after all participants have completed Visit 4 (Day 29) or have withdrawn from the study. A final analysis will occur after all participants have completed Visit 6 (Day 181) or have withdrawn from the study.

3.2 Analysis Populations

The following populations are defined:

Table 1 Populations for Analysis

Population/Analysis set	Description
Screened Set	All participants who provided the Informed Consent
Full analysis set (FAS)/ Safety analysis set	All randomized participants who received part or all of study intervention. Participants in the FAS will be classified according to the assigned treatment. The safety analysis set will include participants from the FAS but report participants according to the actual treatment received regardless of the assigned treatment.
SARS-CoV-2 neutralizing antibody analysis set	All participants in the FAS with baseline and post-dose antibody measurements (i.e. at least one post-dose antibody measurement with a measurable SARS-CoV-2 titer in serum). Participants will be classified according to the actual received treatment. Participants with protocol deviations that may interfere with generation or interpretation of an antibody response may be excluded or have data collected after the protocol deviations set to missing.

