3.3.4 Multiplicity/Multiple Comparisons

All analyses will be performed in descriptive manner, no hypothesis testing will be performed.

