4.1.2.2 Presentation

The number of participants included in each analysis set will be reported by treatment arm. In addition, for each analysis set, the number of participants excluded, including the reasons, will be reported.

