4.2.2 Secondary Endpoint - SARS-CoV-2 Neutralizing Antibody Assessments

4.2.2.1 Definition

Serum samples to measure SARS-CoV-2 Neutralizing Antibody (nAb) levels will be collected according to planned visits. Authorized laboratory will measure nAbs to the SARS-CoV-2 emerging dominant variant(s) circulating during the course of the study.

The SARS-CoV-2 nAb responses include the nAb titer levels and fold rise of nAb titers collected over time. The fold rise will be calculated as the ratio of the post-dose titer and the baseline nAb titer levels.

This secondary endpoint will be analyzed in the SARS-CoV-2 neutralizing antibody analysis set.

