4.2.2.2 Derivations

The geometric means will be calculated as the mean of the assay results after taking the logarithm transformation and then anti-logarithm transformation the mean to express results on the original scale. Two-sided 95% CIs will be obtained by taking log transforms of assay results, calculating the 95% CI with reference to Student's t-distribution, and then anti-logarithm transforming the confidence limits.

Geometric mean fold rises (GMFRs) will be reported and limited to participants with non-missing values at both time points.

Dealing with missing and undetectable results (<LLOQ and >ULOQ) described in Appendix C. Participants who experience an important protocol deviation that can interfere with an antibody response or violate adherence to the assigned dose, become infected, receive COVID-19 treatment or vaccination that can alter nAb levels will have data collected after the intercurrent event set to missing for analysis of this endpoint (i.e., while-on-treatment strategy is applied).

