4.2.2.3 Analysis

GMT and GMFRs, corresponding gSD, 2-sided 95% CIs, minimum and maximum will be presented for each visit by treatment arm in tables separately each dominant variant of SARS-CoV-2. Also box and whiskers plots (separately for each dominant variant) will be presented in the following manner: dots show geometric means, lines within boxes are medians, box bounds are quartiles and whiskers are minimums and maximums.

Also all data will be presented in listings.

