APPENDIX C MISSING DATA ON NEUTRALIZING ANTIBODIES

The analysis of GMTs will use the following imputation methods:

- Missing titer values will not be imputed.
- Titer values measured below the LLOQ will be imputed with half the LLOQ in summaries and analyses but will be listed as reported in the raw data listings.
- Titer values measured above the ULOQ will be imputed at the ULOQ value.

[figure not shown]

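### The neutralizing-antibody set requires an undefined "measurable" post-dose titer; read as at or above LLOQ, it drops participants on the outcome and can only raise, never lower, an arm's GMT

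*SAP*

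**What the plan says.** SAP Table 1 (Section 3.2) and protocol Table 8 (Section 9.3) define the nAb analysis set in the same words. A participant must be in the full analysis set and have baseline and post-dose antibody measurements. A parenthesis introduced by *i.e.* then adds: "at least one post-dose antibody measurement with a measurable SARS-CoV-2 titer in serum".

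This is the only set planned for the nAb endpoint. SAP 4.2.2.1 states: "This secondary endpoint will be analyzed in the SARS-CoV-2 neutralizing antibody analysis set". Protocol 9.4.2.2 says the same.

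SAP Appendix C covers results outside the quantification range: "Titer values measured below the LLOQ will be imputed with half the LLOQ in summaries and analyses". Values above ULOQ are set to ULOQ, and missing titers are not imputed.

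SAP 4.2.2.3 asks for GMT and GMFR by visit and arm, in separate tables for each dominant variant.

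**The concern.** A measurement *with a measurable titer* reads as asking for more than a measurement. On the plain reading the extra condition is a titer at or above LLOQ. Membership then depends on the outcome being summarised: a participant who attended every visit and was below LLOQ at each one is left out. Appendix C would impute half the LLOQ only for participants who reached LLOQ at some other post-dose visit.

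Comparing nAb responses between arms is a stated secondary objective, and protocol 4.2 treats neutralizing activity as the standard surrogate for efficacy in this class. Placebo participants receive no antibody and were selected for risk of a poor immune response, so they are the more likely to be dropped. That would raise the placebo GMT and shrink the contrast. The direction is not guaranteed: if a variant escaped AZD3152, the same rule could drop AZD3152 participants and flatter the product.

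Two programmers could also build different sets from this sentence. It does not say whether *measurable* is judged for each variant or across all of them, although the tables are made per variant.

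**Working it through.** **Inputs from the documents.** Placebo arm n = 29 (protocol synopsis). Five scheduled post-dose nAb samples, on Days 8, 15, 29, 91 and 181 (protocol Table 1). Values below LLOQ become LLOQ/2 (SAP Appendix C). GMT is the antilog of the mean log titer (SAP 4.2.2.2). The plan states no nAb figure to reproduce: no LLOQ, titer distribution, expected GMT or expected share below LLOQ.

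**Direction.** Suppose a share f of an arm is below LLOQ at every post-dose visit, and the participants kept have GMT m × LLOQ at a given visit. With everyone included,

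GMT(all) = LLOQ × m^(1−f) × 0.5^f.

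With the share f excluded, GMT(kept) = LLOQ × m. So

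GMT(kept) / GMT(all) = (m / 0.5)^f.

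No value can fall below LLOQ/2 after imputation, so m ≥ 0.5 and the ratio is never below 1. It equals 1 when f = 0.

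**Size.** The quantities m and f move together: the lower the titers, the more participants are excluded and the lower the GMT of those kept. They were therefore linked by simulation, with 400,000 participants, no treatment effect, a baseline and five post-dose visits. Participants below LLOQ at all five were excluded. The assumptions, none taken from the documents, are log2 SD 2, within-person correlation 0.8, and the true median shown.

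| True median (× LLOQ) | Excluded | Expected of 29 | Kept Day 29 GMT (× LLOQ) | Kept / all |
|---|---|---|---|---|
| 32 | 0.1% | 0.0 | 32.13 | 1.003 |
| 8 | 1.6% | 0.5 | 8.32 | 1.045 |
| 4 | 5.3% | 1.5 | 4.52 | 1.125 |
| 2 | 14.0% | 4.1 | 2.68 | 1.265 |

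The closed form agrees. For the last row, (2.68 / 0.5)^0.140 = 1.265. For the 4 × LLOQ row, (4.52 / 0.5)^0.053 = 1.124.

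**Range.** Varying the SD from 1.5 to 2.5 and the correlation from 0.8 to 0.95, the ratio runs over 1.00–1.05 (median 32), 1.01–1.23 (median 8), 1.05–1.42 (median 4) and 1.17–1.68 (median 2). The GMFR ratio is at most 1.03 throughout, because an excluded participant is usually low at baseline too.

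**Fewer visits.** At the interim analysis the last participants will have only Days 8, 15 and 29, and titers after an intercurrent event are set to missing. With three post-dose visits and the base assumptions, the ratios at medians of 8, 4 and 2 become about 1.07, 1.18 and 1.37. Membership of the set could also change between the interim and final analyses.

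**The case against.** The strongest reply is that *measurable* may mean only that a result was obtained. The phrase sits after *i.e.*, so it can be read as explaining what a post-dose measurement is. Appendix C speaks of titers measured below the LLOQ and wants them in the summaries, which suggests they should count. On that reading nobody is dropped and there is no bias. This stands as a possible reading, but nothing in the text settles it. SAP 4.2.2.2 does not help: "Dealing with missing and undetectable results (<LLOQ and >ULOQ) described in Appendix C" applies the same label to results at both ends of the range.

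The size rests wholly on assumed inputs. Obesity, heart failure or COPD alone qualifies a participant (protocol 5.1), and vaccination or infection more than 6 months earlier is allowed (protocol 5.2), so few or none may be below LLOQ throughout. In the base model at a median of 8 × LLOQ, the chance that no placebo participant is excluded is (1 − 0.016)^29, about 63%. The shift is also modest against the planned precision: with log2 SD 2 and n = 29, the 95% half-width is 2.048 × 2 / √29 = 0.76 log2 units, a factor of about 1.7 either way before censoring. That is fair context, though interval width does not remove a systematic error.

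There are safeguards. SAP 3.3.4 says "All analyses will be performed in descriptive manner, no hypothesis testing will be performed". Under SAP 4.1.2.2, for each set, "the number of participants excluded, including the reasons, will be reported". SAP 4.2.2.3 adds: "Also all data will be presented in listings". If placebo is the affected arm, the error works against the product. Primary safety and COVID-19 incidence use other sets. All of this limits the consequence, but it discloses an exclusion without correcting the tabulated GMT.

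**Conclusion.** The concern holds, as a minor one. The inclusion condition is undefined in both documents. On its plain reading it selects on the outcome, and the direction follows by arithmetic: the arm's post-dose GMT is raised or unchanged, with placebo the likelier arm. Under the base assumptions the Day 29 overstatement runs from negligible at a median of 32 × LLOQ to about a quarter at 2 × LLOQ. Other assumed SDs and correlations widen this to 1.00–1.68 over the same medians. The effect is zero if nobody is below LLOQ at every post-dose visit, or if *measurable* was meant only as a result obtained. GMFR is nearly unaffected.

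**What to change.** In SAP Table 1, replace the condition with: *a baseline result and at least one valid post-dose assay result, including results below LLOQ or above ULOQ*. State that membership does not depend on the titer value for any variant, and that Appendix C applies to these participants. Make the same change in protocol Table 8 at the next amendment.

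The two documents agree at present, so there is no existing lapse to record. Changing the SAP first creates a difference, and SAP Section 1 says "All discrepancies with the CSP should be clarified", so enter it in SAP Section 2. A table of the percentage below LLOQ by arm, visit and variant would be a useful option.

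The cost is one sentence and one entry, with no new data. The placebo GMT may come out lower and rest on more imputed values. If any result was always what was meant, the edit changes nothing except to remove the doubt.

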3.3 General Considerations

The data analyses will be conducted using SAS® System (SAS Institute Inc., Cary, NC), version 9.4 or higher.

In general, all data will be listed, sorted by treatment arm and participant, and when appropriate by visit number within participant.

Unless otherwise noted, data will be presented in tables by treatment arm (i.e. AZD3152 and placebo) using descriptive statistics.

3.3.1 General Study Level Definitions

The study will consist of 2 periods: a screening period of up to 7 days (Day -7 through Day -1), and a treatment and follow-up period lasting 6 months after the administration of study intervention which consist of Visit 1 (Day 1), Visit 2 (Day 8), Visit 3 (Day 15), Visit 4 (Day 29), Visit 5 (Day 91) and Visit 6 (Day 181). Acceptable visit windows presented in Section 3.3.2. More detailed description of study visits and procedures presented in the Schedule of Activities (Table 1) of the CSP.

Categorical variables will be summarized using frequency, percentages (where the denominator for calculation is the underlying analysis set population, unless otherwise stated).

Continuous (quantitative) data will be presented as:

- Number of valid observations (n);
- Arithmetic Mean (M) or Geometrics Mean (gM) if appropriate;

- Standard deviation (SD) or Geometric standard deviation (gSD) if appropriate;
- 95% confidence interval (CI) if appropriate;
- Minimum value (Min.);
- Maximum value (Max.);
- Median (Me);

Data after log transformation will be rounded up to 3 decimals.

For continuous data, descriptive statistics will be rounded according to rules:

Mean, geometric mean, median and quartiles will be represented with an accuracy of 1 decimal place greater than the measured values. Standard deviation and geometric standard deviation will be represented with an accuracy of 2 decimal places greater. Minimum and maximum will have the accuracy of the measured values.

For categorical data, percentages will be rounded to 1 decimal place.

Data will be provided in data listings sorted by treatment arm and participant number. Tabular summaries will be presented by the actual treatment received for safety analysis and by the assigned for efficacy analysis.

3.3.2 Visit Window

Period	Visit	Nominal Day	Windows			
			SARS-CoV-2 serology	SARS-CoV-2 nAb serum samples	Laboratory assessments	Vital signs
Screening	Screening	(-7) – (-1)	(-7) – (-1)	(-7) – (-1)	(-7) – (-1)	(-7) – (-1)
Treatment and Follow-up Period	Visit 1	1	1	1	1	1
	Visit 2	8	–	5 – 11	2 – 18	2 – 94
	Visit 3	15	–	12 – 18	–	–
	Visit 4	29	2 – 60	26 – 32	19 – 195	–
	Visit 5	91	61 – 136	86 – 96	–	–
	Visit 6	181	137 – 195	167 – 195	–	95 – 195

When one or more results are available for the same visit window, the result with the date closest to the expected visit date will be used in the analysis. If two observations are equidistant from the expected visit date, the later observation will be used in the analysis. Visits outside the specified visit windows will not be part of the by-visit summaries (i.e., no mapping will be applied to such data points).

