### 1.3.1 Screening, Treatment and Follow-up Activities

Table 1 Schedule of Activities

Procedure	Screening	Treatment and Follow-up Period						
		1	2	3	4	5	6	EDV
Visit	Screening	1	2	3	4	5	6	
Day	-7 to -1	1	8	15	29	91	181	NA
Window (days)	NA	NA	± 3	± 3	+ 3	± 5	± 14	NA
Written informed consent	X							
Verify eligibility criteria	X	X (predose)						
Randomization		X (predose)						
Medical history and demographics (including COVID-19 vaccine status and previous COVID-19 infection)	X							
Full physical examination, including height and weight	X							X
Targeted physical examination based on medical history		X (predose)						
Vital signs	X	X a	X			X		X
Serum chemistry, hematology, coagulation (local laboratory)	X		X		X			X
Troponin, high-sensitivity test (local laboratory)	X b							

Procedure	Screening	Treatment and Follow-up Period						
		1	2	3	4	5	6	EDV
Visit	Screening	1	2	3	4	5	6	EDV
Day	7 to 1	1	8	15	29	91	181	NA
Window (days)	NA	NA	± 3	± 3	+ 3	± 5	± 14	NA
Follicle stimulating hormone c	X							
HIV test	X							
Electrocardiogram (single, to be performed locally if feasible) d	X							
Urine pregnancy test or serum β-hCG (WOCBP only)	X	X e						
Rapid antigen test for SARS-CoV-2 (performed locally)		X f						
Weekly telephone/email/text contacts-monitoring for safety and COVID-19 qualifying symptom					X			
Assessment of AEs				X				X
Assessment of SAEs, MAAEs, and AESIs	X (SAEs)				X (ongoing observation and questioning)			X
Concomitant medications	X				X (ongoing observation and questioning)			X
CCI [REDACTED]		X (predose)			X	X	X	X

Procedure	Screening	Treatment and Follow-up Period						
		1	2	3	4	5	6	EDV
Visit	Screening	1	2	3	4	5	6	EDV
Day	7 to 1	1	8	15	29	91	181	NA
Window (days)	NA	NA	± 3	± 3	+ 3	± 5	± 14	NA
SARS-CoV-2 nAb serum sample h		X (predose)	X	X	X	X	X	X
CCI		X (predose)			X	X	X	X
Study intervention administration		X						
Injection site reaction monitoring		X j	X					
Immediate AEs k		X						

a On dosing day, vital signs will be performed predose and again approximately 10 to 15 minutes after injection. Any abnormal vital signs must be repeated after the participant has been at rest for at least 5 minutes.

b It is acceptable for this to be performed on Day 1 (predose). Test results must be available prior to dosing.

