4.3.4 Vital Signs

4.3.4.1 Definitions and Derivations

The following vital signs (VS) will be measured according to Section 8.2.2 of the CSP: pulse rate, respiratory rate, blood pressure, and body temperature.

For multiple VS assessments on Visit 1 the following rules will be used for analysis:

- If a participant has multiple VS assessments before IMP dosing, then the last assessment before dosing should be used as baseline and included into the table, but all records should be reported in a listing
- If a participant has multiple VS assessments after dosing then:
 - If a participant has record in "10-15 min window after dosing" then this record should be included in analysis as correct assessment
 - If a participant does not have records in "10-15 min window after dosing" then the first post-dosing assessment should be included in analysis

For multiple VS assessments on Visits 2 and 6 the earliest assessment within a visit window will be used for analysis.

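### The protocol schedule puts the last on-study vital signs at Visit 5 (Day 91), but the SAP windows assume Visit 6 (Day 181), so a Day 91 reading has no row of its own in the by-visit tables

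*SAP*

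**What the plan says.** **Protocol, section 1.3.1, Table 1.** The vital-signs row reads "Vital signs X X a X X X". Set against the column headings, with the blank cells counted, the marks fall at Screening, Visit 1, Visit 2, Visit 5 and the early discontinuation visit. Visits 3, 4 and 6 are blank. The day row is "Day -7 to -1 1 8 15 29 91 181 NA" and the window row is "Window (days) NA NA ± 3 ± 3 + 3 ± 5 ± 14 NA", so Visit 5 is Day 91 ± 5. Protocol 8.2.2 adds no visit list and refers back to this schedule.

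**SAP, section 3.3.2.** In the window table the last column is vital signs. The Visit 2 row is "Visit 2 8 – 5 – 11 2 – 18 2 – 94" and the Visit 6 row is "Visit 6 181 137 – 195 167 – 195 – 95 – 195". The Visit 5 row is "Visit 5 91 61 – 136 86 – 96", followed by dashes for laboratory assessments and vital signs.

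**SAP, section 4.3.4.1.** The rule for repeated readings opens "For multiple VS assessments on Visits 2 and 6" and takes the earliest in the window. Section 3.3.2 has a different general rule: the reading closest to the expected visit date.

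**Declared differences.** SAP section 1 asks for discrepancies with the protocol to be clarified, and section 2 declares no change. The amendment history marks the February 2024 addition to 4.3.4.1 as in line with the protocol.

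**The concern.** Protocol 9.4.3 and SAP 4.3.4.2 both promise vital signs by arm and visit, with changes from baseline. Apart from the early discontinuation visit, Table 1 as read has one scheduled vital-signs check after Day 8, at Day 91. The SAP windows have nowhere to put it. Most such readings would compete with the Day 8 reading inside a window that runs to Day 94, and the others would appear under a visit about three months later. The report would then have a Day 181 row at which Table 1 schedules no vital signs, and no Day 91 row. Safety is the primary objective, so the descriptive safety tables should show each reading under the visit at which it was taken.

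**Working it through.** **Inputs.** Protocol Table 1: Visit 2 = Day 8 ± 3 (Days 5–11); Visit 5 = Day 91 ± 5 (Days 86–96, 11 days); Visit 6 = Day 181 ± 14. SAP 3.3.2, vital signs: Visit 2 = Days 2–94; Visit 6 = Days 95–195. Protocol 9.2: 116 randomized, about 5% drop-out.

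**1. Where the SAP boundary comes from.** The SAP does not state a rule, but its wide windows all split at the midpoint of adjacent visit days, rounded down:

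| Assessment | Midpoint | SAP boundary |
|---|---|---|
| Serology, Visits 4 and 5 | (29 + 91)/2 = 60 | 60/61 |
| Serology, Visits 5 and 6 | (91 + 181)/2 = 136 | 136/137 |
| Laboratory, Visits 2 and 4 | (8 + 29)/2 = 18.5 | 18/19 |
| Vital signs, Visits 2 and 6 | (8 + 181)/2 = 94.5 | 94/95 |

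The vital-signs boundary is reproduced by pairing Visit 2 with Visit 6. Pairing Visit 2 with Visit 5 would give (8 + 91)/2 = 49.5. The SAP windows were therefore built on a Visit 6 schedule.

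**2. Whether the Table 1 row can be trusted.** The table was machine-read. The vital-signs row has all eight cells. Counted the same way, the chemistry row, "Serum chemistry, hematology, coagulation (local laboratory) X X X X", falls at Screening, Visit 2, Visit 4 and early discontinuation, which matches the SAP laboratory windows at Visits 2 and 4. The neutralizing-antibody row is marked in every column from Visit 1 on, so it cannot reveal a shifted mark and is no check.

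**3. Where Visit 5 readings go under the SAP windows.**

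- Days 86–94 (9 of 11 days, 82%, including Day 91 itself) lie in the Visit 2 window.
- Days 95–96 (2 of 11 days, 18%) lie in the Visit 6 window.

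**4. Which reading is kept in the Visit 2 window.** An on-schedule Visit 2 reading is at most 3 days from Day 8. A Visit 5 reading is at least 86 − 8 = 78 days from it. The Visit 2 reading wins in all 7 × 9 = 63 day combinations under the closest-date rule, and always under the earliest rule. If the participant has no other reading in Days 2–94, the Visit 5 reading is kept and tabulated as Day 8.

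**5. Mislabelling in the Visit 6 window.** 181 − 95 = 86 and 181 − 96 = 85, so these readings appear 85 or 86 days late.

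**6. Size.** Attending: 116 × 0.95 ≈ 110. Attendance within the window is not given, so it is assumed:

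| Attendance over Days 86–96 | Share labelled Day 181 | Readings of 110 | In the Visit 2 window |
|---|---|---|---|
| Even | 2/11 = 18% | 20 | 90 |
| Normal around Day 91, SD 3 days | 9.4% | 10 | 100 |
| Same, SD 2 days | 3.6% | 4 | 106 |
| Same, SD 1 day | 0.01% | 0 | 110 |

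The more visits cluster around Day 91, the fewer are labelled Day 181 and the more fall into the Visit 2 window.

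**The case against.** The protocol side rests on the position of one mark in a machine-read table, and no protocol prose says that vital signs are taken at Day 91. The SAP side rests on two separate statements and a boundary that fits only Visits 2 and 6, and the rule added in February 2024 still names Visit 6. If the mark was displaced by one column, or if sites in fact collected vital signs at Visit 6 and not at Visit 5, the SAP windows work and nothing is lost. The chemistry row makes a displaced mark less likely but does not rule it out. This stands: the contradiction is in the documents as read, and its consequence is conditional on the schedule in use.

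The impact is also limited. Vital signs are neither a primary nor a secondary endpoint, all analyses are descriptive, every reading is listed (SAP 4.3.4.2), and deterioration judged clinically relevant is reported as an adverse event (protocol 8.3.7). This stands too. It limits the harm to the by-visit tables but does not make those tables right.

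A reader might infer that the Day 91 data are certainly lost, or that the SAP is the document in error. Neither follows. The documents do not show which visit was intended, and the raw values stay in the listings whatever the windows.

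**Conclusion.** The protocol schedule and the SAP disagree on the late vital-signs visit, and the SAP does not declare the difference. If Table 1 as read is what sites follow, the SAP windows give wrong by-visit tables. Of about 110 Visit 5 readings, roughly 90 to 110 fall in the Visit 2 window, where each is left out if an on-schedule Day 8 reading exists and shown as Day 8 if it is the only reading there. Roughly 0 to 20 are shown as Day 181. These figures assume 5% drop-out and attendance ranging from even over the 11 days to tightly clustered around Day 91. A single split of 90 and 20 is tempting but holds only for even attendance.

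The by-visit summaries and change-from-baseline tables for vital signs are affected. Listings, adverse event tables and the other assessments' windows are not. The point is worth correcting because the rule as written cannot produce a Day 91 row and the correction is cheap, but it does not threaten the primary adverse event analysis.

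**What to change.** First reconcile Table 1 with SAP 3.3.2 and 4.3.4.1 against the schedule actually used for data collection. Removing the Visit 6 row before that check could drop valid readings. Then:

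- **If Visit 5 stands:** rebuild the vital-sign windows by the midpoint rule, Visit 2 = Days 2–49 and Visit 5 = Day 50 onward. Remove the Visit 6 vital-sign row, and name Visits 2 and 5 in 4.3.4.1. Keep early-discontinuation readings mapped by window, as SAP 3.3.3 already provides.
- **If Visit 6 was intended:** correct the mark in Table 1 and leave the SAP windows as they are.
- **If both were intended:** correct Table 1, use Days 2–49, 50–136 and 137–195, and name all three visits in 4.3.4.1.

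In the first and third cases all 11 days of the Visit 5 window map to Visit 5. While editing, state one selection rule for repeated readings, since 3.3.2 and 4.3.4.1 differ. The cost is a few lines of SAP text and the matching window definitions in the programs, or a one-cell correction to the schedule. No new data are needed if Table 1 stands.
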